3. METHODS

This section contains information about the study design and statistical analysis that will be performed to assess the hypotheses.

3.1. Study Design

We conducted a randomized controlled trial among 216 AYA in Almaty, Kazakhstan. Participants were randomized 1:1 to the intervention or control arm. Participants randomized to the intervention arm viewed AYA-crowdsourced digital materials (video, audio, images, text) over a five-week period. Participants randomized to the control arm viewed existing multi-media materials obtained from Kazakhstani health organizations over the same period. Intervention and control materials were administered online through weekly emails via Qualtrics for five weeks (after baseline survey (week 0) to the one-month follow-up (week 4)), with content scheduled to be delivered at the same time on a weekly basis (2-3 items shown per week). Viewing length of weekly content was approximately 5-10 minutes. We varied weekly content by type (video, image, text) and aimed to match control content by type and length to the intervention content. Participants in both arms were assessed at three time points: baseline “pre-intervention”, immediately post-intervention (one-month follow-up), and three-month follow-up.

3.2. Trial Randomization

A research assistant (RA) assigned participants 1:1 to the intervention or control arm using a computer-generated randomization sequence and scheduled the participants to receive surveys and their assigned intervention or control content. AYA were blinded to their arm assignment and did not know whether they were receiving intervention or control materials.

3.3. Data Sources

3.2.1. Participant Surveys

Participants completed online surveys via Qualtrics at three timepoints -- baseline “pre-intervention”, immediately post-intervention (one-month follow-up), and three-month follow-up. Among the many topics assessed, surveys included sociodemographic items, the HIV stigma scale,¹ and a link to an online form to order an HIV self-test kit.

3.2.2. HIV Self-Testing Uptake

AYA who clicked on the survey link could fill out an online form to order an HIV self-test kit. The kit could be mailed to their home address or another location of their choosing, or ordered for pick-up at a local non-governmental organization. Participants sent pictures of their self-test results via WhatsApp to an RA. Participants who screened positive for HIV would be referred to a youth clinic and the Almaty City AIDS Center for confirmatory testing. However, none of our participants screened positive for HIV.

3.4. Statistical Interim Analysis and Stopping Guidance

There are no interim analyses or interim stopping rules that must be considered for this statistical analysis plan (SAP).

3.5. Sample Size

Power analyses were conducted with G*Power (v3.1.0) based on the primary outcome of HIV stigma reduction using a Wilcoxon-Mann-Whitney test approach and $\alpha=.05$. With 108 participants per arm, we would have 80% power to detect a small-to-medium effect size ($d=0.39$).

4. STATISTICAL PRINCIPLES AND ANALYSIS

4.1 Confidence Intervals and P-values

All statistical computations will be performed by the PI ([name]), who is an epidemiologist, in consultation with quantitative data scientists. For descriptive summaries of study data, the following will be presented:

- Nominal/categorical measures will be summarized using frequencies and percentages;
- Interval or ratio scale measures will be summarized using means and standard deviations;
- Ordinal measures will be summarized depending on the number of levels. An ordinal measure with five levels or less will be summarized as a nominal measure. An ordinal measure with more than five levels will be summarized as an interval or ratio scale measure.

The balance or imbalance of baseline characteristics will be studied and reported, particularly for analyses comparing the two study arms.

Reported p-values will be based on two-sided tests at an $\alpha=0.05$ unless otherwise specified. When p-value correction is appropriate, Benjamini-Hochberg² False Discovery Rate adjustments will be used to address multiplicity and preserve Type I error rate.

Unless required otherwise by a journal, the following rules are standard:

- Test statistics will be reported to two decimal places.
- P-values will be reported to two significant figures. If less than 0.001, p-values will be reported as ' <0.001 '.
- No preliminary rounding will be performed; rounding will only occur after analysis. To round, consider digit to right of last significant digit: if < 5 round down, if ≥ 5 round up.

4.2. Dependent Variables

The dependent variables in this analysis are:

1. Self-Reported HIV Stigma – Assessed by a 17-item HIV stigma scale that was originally developed for community members not living with HIV in South Africa and Zambia.¹ The scale was reviewed by our Community Collaborative Research Board (CCRB), and we conducted cognitive interviews with 10 Russian-speaking AYA and nine Kazakh-speaking AYA. AYA and our CCRB provided feedback on the cultural and age-appropriateness of the items, and gave recommendations on item modification. Item response options were on a five-point Likert scale (1 – strongly disagree to 5 – strongly agree). The total score across the 17 items was calculated, with a maximum total score of 85. Scale reliability was high in our sample ($\alpha=.871$).

2. HIV Self-Testing Uptake – Number of AYA in each arm who ordered an HIV self-test kit in the follow-up period after the pre-intervention assessment.

4.3. Independent Variables

The key independent variables in this analysis are:

Study Arm – Randomized to the Intervention arm or the Control arm.

Timing of Assessment – baseline (pre-intervention), immediately post-intervention (one-month follow-up), three-month follow-up.

4.4. Covariates

As appropriate in the analyses, multivariable modeling of changes in HIV stigma will include adjustment for the following participant-level characteristics:

- a. Age
- b. Sex
- c. Sexual orientation
- d. Baseline levels of HIV stigma
- e. Submission of crowdsourcing entry to the JasSpark study contest
- f. Prior HIV testing (baseline and prior to the study)

4.5. Statistical Analysis Methods

Descriptive statistics of key independent variables and covariates will be summarized within each arm using frequencies or means (standard deviations) as appropriate. Overall participation rates will be reported in each arm based on the proportion of baseline participants who completed the three-month follow-up assessment.

To test **hypothesis 1 (H1)**, we will conduct multilevel linear mixed models to assess for differences in changes in the overall HIV stigma score between study arms. As a secondary analysis, we will also assess changes in each of the stigma subscale scores (perceived stigma in the community, fear and judgement, perceived stigma in healthcare settings, and HIV testing stigma). To account for multiple comparisons arising from analyses of subscales, the false discovery rate (FDR) was controlled using Benjamini-Hochberg procedures in a tiered approach.²

To test **hypothesis 2 (H2)**, we will use a generalized linear model using a binomial distribution to examine whether the intervention was associated with increased HIV self-testing uptake in the follow-up period. The model was adjusted for history of HIV testing (pre-intervention testing and testing prior to the study), whether the participant had submitted content to the JasSpark contest, and if the participant had a main intimate partner (e.g., girlfriend/boyfriend, spouse).

To test **hypothesis 3 (H3)**, we examined potential moderation effects of sex at birth on stigma changes. Fixed effects corresponding to the two-way interactions involving sex, time, and/or arm, as well as the three-way interaction of sex, time, and arm, were added to the models from

H1. To account for multiple comparisons arising from analyses of moderating effects, the false discovery rate (FDR) was controlled using Benjamini-Hochberg procedures in a tiered approach.²

The model testing H3 is summarized as Equation H3:

HIV stigma score = Intercept + B₁(Arm) + B₂(Categorical variable corresponding to timepoint of stigma assessment; two degrees of freedom) + B₃ (Arm * Timepoint of stigma assessment; two degrees of freedom) + B₄(Baseline stigma level) + B₅(Respondent Sexual orientation) + B₆(Respondent Age) + B₇ (Respondent Sex) + B₈ (Respondent Submitted entry to JasSpark contest) + B₉ (Respondent HIV testing prior to study) + B₁₀ (Respondent HIV testing baseline) + Error
+ Random effects for the clustering within participant across timepoints and by dyad.

If the statistical test for the interaction between arm and timepoint is significant at the $\alpha=0.05$ level, then we conclude that study arm significantly impacts the change in HIV stigma. Within arm, adjusted estimates of changes in adherence will be presented along with 95% confidence intervals.

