4.6. Missing Data

The analysis sample is restricted to participants with data for the outcomes and with key demographic information. Missing data for outcomes or demographics will not be imputed.

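### With complete data, the baseline-stigma covariate in Equation H3 cancels from the tested arm-by-timepoint term, leaving a valid but unadjusted change-score contrast that gives up precision

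*SAP*

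**What the plan says.** - SAP 4.3 lists the assessment times as "baseline (pre-intervention), immediately post-intervention (one-month follow-up), three-month follow-up". Equation H3 in SAP 4.5 gives timepoint, and arm by timepoint, two degrees of freedom each. Baseline is therefore one of the three outcome rows.
- SAP 4.4 lists "Baseline levels of HIV stigma" among the adjustment covariates. Equation H3 enters it as a single term with no time interaction: "two degrees of freedom) + B₄(Baseline stigma level". B5 to B10 (sexual orientation, age, sex, contest entry, two HIV-testing items) are also main effects only.
- The last line of the equation gives "Random effects for the clustering within participant across timepoints and by dyad".
- The decision rule at the end of SAP 4.5 begins "If the statistical test for the interaction between arm and timepoint is significant".
- On which hypothesis the equation serves, the SAP states "The model testing H3 is summarized as Equation H3". The preceding text describes sex interactions, "as well as the three-way interaction of sex, time, and arm, were added to the models from" H1, yet the printed equation contains none. It therefore looks like the H1 model, but no equation carries that label.
- On missing data, SAP 4.6 says "The analysis sample is restricted to participants with data for the outcomes", without saying whether all three scores are required.
- SAP 1 and Protocol 3.3.11 define the primary effect as follow-up minus baseline stigma, compared between arms.

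**The concern.** Using one measurement as both a response and a predictor in the same model is unusual, and the first question is what it does to the tested term. A covariate that is constant within a participant and has no time interaction can shift that participant's overall level but not the change over time. The test is on the change over time.

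Two things are at stake. A reader of SAP 4.4 and 4.5 would take the primary stigma test to be adjusted for baseline stigma and the other listed characteristics when, for the equation as printed with complete rows, it is not. And a pilot whose stated purpose is preliminary effect estimates would report a wider interval than its own data allow.

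**Working it through.** **The plan's own figure.** Inputs from SAP 3.5 and 4.1: 108 per arm, d = 0.39, Wilcoxon-Mann-Whitney, two-sided alpha 0.05. With the normal-parent efficiency 3/π, the effective n is 108 × 3/π = 103.1 per arm. Then 0.39 × √(103.1/2) = 2.80, and power is Φ(2.80 − 1.96) = 80%. The stated power reproduces.

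**Cancellation.** Split each participant's three scores into their mean and two within-person differences (month 1 minus baseline, month 3 minus baseline). With random intercepts for participant and dyad and complete rows, the mean and the differences carry separate information. Every time-constant term (B4 to B10, the arm main effect, the random intercepts) enters only the mean. Arm by timepoint is estimated only from the differences, so its month-3 component is exactly

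(mean of month 3 − baseline, intervention) − (mean of month 3 − baseline, control).

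**Numerical check.** REML random-intercept fits to one simulated trial, 108 per arm, correlation 0.5, prognostic B5 to B10:

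| Model | Arm × month 3 | SE |
|---|---|---|
| No covariates | −0.12696 | 0.13466 |
| With B4 | −0.12696 | 0.13466 |
| With B4 to B10 | −0.12696 | 0.13466 |
| Raw difference in mean change | −0.12696 | |

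In a second simulated trial with the sex interactions added, arm × month 3 was 0.07207 (SE 0.1937) with and without B4. Sex itself no longer drops out of that larger model; B4 still does.

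**Partial rows.** If participants with a missing score are kept, cancellation is only approximate. With 20% of month-3 scores missing at random (assumed), B4 moved the estimate by 0.018, 0.016 and 0.013 score SD on average at correlations 0.3, 0.5 and 0.7. Its true spread did not fall: 0.173, 0.150, 0.114 without B4 and 0.174, 0.152, 0.115 with it.

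**Precision given up, complete rows.** Let ρ be the correlation between baseline and month-3 scores. It is not in the documents; I assume 0.3, 0.5 and 0.7 and equal variances σ².

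- Change-score variance per participant: 2σ²(1 − ρ).
- Baseline-adjusted variance: σ²(1 − ρ²).
- Ratio: 2/(1 + ρ).

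| ρ | Variance ratio | 95% half-width, written vs adjusted (score SD) |
|---|---|---|
| 0.3 | 2/1.3 = 1.54 | 0.32 vs 0.26 |
| 0.5 | 2/1.5 = 1.33 | 0.27 vs 0.23 |
| 0.7 | 2/1.7 = 1.18 | 0.21 vs 0.19 |

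**Power for the one-df three-month contrast.** Take d = 0.39 in SD units of the change, the reading closest to SAP 3.5, and a t-based test. Unadjusted, the noncentrality is 0.39 × √(108/2) = 2.87, giving 81% at every ρ (the Wilcoxon discount accounts for the SAP's 80%). Adjusted, d becomes 0.39/√((1 + ρ)/2) = 0.484, 0.450, 0.423, giving 94%, 91%, 87%. If 0.39 is instead in SD units of the score, the pairs are 67% vs 85%, 81% vs 91% and 96% vs 98%. These figures do not apply to the two-df interaction test.

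**The case against.** The strongest reply is that the plan delivers what it promises. Protocol 3.3.11 and SAP 1 define the effect as a difference in change scores, and the interaction term estimates exactly that. The planned power holds, and preferring an adjusted analysis is a choice of efficiency over simplicity. This stands as far as validity goes, and it is why keeping the written contrast remains acceptable if it is described correctly. It does not explain why B4 is in the equation or why SAP 4.4 lists baseline stigma as an adjustment for models of change.

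SAP 4.4 also qualifies its list with the words as appropriate, and no equation is labelled as the H1 model. A reader might infer that the stigma test is adjusted for none of the covariates in any version of the model. The documents support that only for the equation as printed, with complete rows; once the sex interactions described for H3 are added, sex does play a part.

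The size of the loss depends on a correlation the documents do not give, and at 0.7 the gain from adjustment is small. That also stands.

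Finally, the SAP already reports results: SAP 3.2.2 states that nobody screened positive, and SAP 4.2 gives the scale's reliability in the sample. A change of primary model now is a late change. That is a reason for disclosure and for showing both estimates, not for leaving an inert term in the equation.

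**Conclusion.** The point holds as one of precision and description, and should be fixed. With all three scores present, B4 and the other main effects as printed have no influence on the tested arm-by-timepoint estimate, which is an unadjusted change-score contrast. That result is exact for the printed model and does not depend on whether Equation H3 is the H1 model. With partial rows retained, B4 shifts the estimate slightly and brings no real gain.

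The variance penalty against a baseline-adjusted three-month contrast is 1.54, 1.33 or 1.18 at assumed correlations 0.3, 0.5 or 0.7, with equal variances. Confidence in the size is moderate, because the correlation and the missingness are unknown.

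Two stronger readings are tempting and should not be drawn. A reader might infer that having baseline on both sides biases the test or makes it invalid; with complete rows the estimate equals the raw difference in mean change, so it does not. A reader might also infer that the trial is underpowered or that the 80% is wrong; the figure reproduces, and what is lost is additional precision above the plan.

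**What to change.** First state which equation is the H1 model and whether participants with one or two scores are kept. Then choose one form:

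- **(a)** Outcome rows at months 1 and 3 only, with arm, time, arm by time, baseline stigma, baseline by time, and the other SAP 4.4 covariates.
- **(b)** Keep the three rows, delete B4, and constrain the arms to a common baseline mean.

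In either form, use an unstructured within-person covariance in place of the participant random intercept, not on top of it: three rows supply 6 variances and covariances for 7 parameters, and two rows supply 3 for 4. Rest the SAP 4.5 conclusion on the three-month arm contrast, which is what SAP 1 and the primary alternative in SAP 2 describe. Under (a), arm by time tests only whether the effect differs between months 1 and 3, so the present rule would no longer test the intervention effect.

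Report the change-score contrast alongside, and disclose that the model was changed after data were seen, so that the choice cannot follow the result.

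If the sponsor keeps the written contrast as primary, the minimum is to drop B4, describe the test as an unadjusted change-score contrast, and report (a) or (b) as a labelled sensitivity analysis.

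No new data are needed. The cost is rewriting the equation, the random-effects line and the decision rule together, plus the disclosure. Under (a), the within-arm changes promised in SAP 4.5 need a separate summary.

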1. INTRODUCTION

The JasSpark study used a community-based participatory approach that engaged local adolescents and young adults (AYA) in Kazakhstan to develop a crowdsourced digital HIV stigma reduction and self-testing intervention to reduce HIV stigma and increase HIV testing among AYA in Kazakhstan. We then pilot tested this crowdsourced HIV stigma reduction and self-testing intervention in a preliminary efficacy trial to assess feasibility and acceptability and obtain preliminary estimates of its effects on decreasing HIV stigma (primary outcome) and increasing HIV testing (secondary outcome) among AYA who received the intervention compared to individuals who did not.

This document outlines the statistical analysis plan that will be followed to assess outcomes.

Primary Outcome: To evaluate the change in HIV stigma score (follow-up stigma score minus baseline stigma score) from baseline to the three-month follow-up between the intervention and control arms.

Secondary Outcome 1: To compare HIV self-testing uptake by the three-month follow-up period between AYA in the intervention and control arms.

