2. HYPOTHESES

The **primary** null (H_0) and alternative (H_A) statistical hypotheses are:

H_{P0} : HIV stigma throughout the three-month follow-up period will not differ between the intervention and control arms.

H_{PA} : HIV stigma at three-months follow-up will significantly decrease in the intervention arm compared to the control arm.

The **first secondary** null (H_0) and alternative (H_A) statistical hypotheses are:

H_{S10} : HIV self-testing uptake by three-months follow-up will not differ between the intervention and control arms.

H_{S1A} : HIV self-testing uptake by the three-month follow-up will be higher in the intervention arm compared to the control arm.

The **second secondary** null (H_0) and alternative (H_A) statistical hypotheses are:

H_{S20} : Changes in HIV stigma from baseline to the three-month follow-up period will not be moderated by sex at birth.

H_{S2A} : Changes in HIV stigma from baseline to the three-month follow-up period will be moderated by sex at birth.

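### The primary stigma question is set at three months, but the only decision rule is a non-directional two-degree-of-freedom test over both follow-up visits, and no between-arm estimate or interval at three months is promised

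*SAP*

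**What the plan says.** SAP section 1 defines the primary outcome as the change in stigma score "from baseline to the three-month follow-up between the intervention and control arms". In SAP section 2 the primary alternative is at the same visit and has a direction: "HIV stigma at three-months follow-up will significantly decrease in the intervention arm compared to the control arm". The primary null is wider: "HIV stigma throughout the three-month follow-up period will not differ between the intervention and control arms". Protocol 3.3.11 speaks of follow-up periods in the plural and singles out no visit.

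SAP 4.3 lists three assessment times: "baseline (pre-intervention), immediately post-intervention (one-month follow-up), three-month follow-up". For H1, SAP 4.5 commits to mixed models "to assess for differences in changes in the overall HIV stigma score between study arms", without naming a visit or a contrast. It prints one equation, with timepoint as a categorical variable and an arm-by-timepoint term on 2 df. The rule that follows is that if this interaction is significant at 0.05, "then we conclude that study arm significantly impacts the change in HIV stigma". The only estimates then promised with 95% intervals are changes within each arm, and they are described as changes in adherence, which is not an outcome of this trial. SAP 4.1 has confidence intervals in its title but promises no between-arm interval.

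The equation is introduced with "The model testing H3 is summarized as Equation H3", yet it contains no interaction involving sex, which H3 needs. It is in effect the H1 model. That the rule decides H1 is therefore an inference, though a natural one, because the rule speaks only of study arm and change in stigma.

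**The concern.** The outcome and alternative ask one question (do the arms differ in change by three months, in favour of the intervention?). The null and the decision rule ask another (do the arms differ in change at either visit, in either direction?). Under SAP 3.1 the content runs from week 0 to week 4, so the one-month visit falls at the end of exposure, and an early effect that fades is plausible. Such an effect could satisfy the rule and be reported as success on the three-month hypothesis. A harmful one-month effect would satisfy it just as often.

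Both documents also say that the pilot is meant to give preliminary effect estimates. The estimate that matches the stated primary outcome, the between-arm difference at three months with its interval, is not among those promised.

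**Working it through.** **1. The plan's own figure.** SAP 3.5 gives 108 per arm, a Wilcoxon-Mann-Whitney test, alpha 0.05, d = 0.39 and 80% power. With relative efficiency 3/π = 0.955, power = Φ(0.39 × √(108 × 0.955/2) − 1.96) = Φ(2.80 − 1.96) = 0.80. It reproduces, as a single two-group comparison and not as a joint test of two visits.

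**2. Set-up for the decision rule.** From the SAP: n = 108 per arm, three visits, 2 df, two-sided 0.05. Assumed, because the documents do not give them: equal between-visit correlation ρ = 0.3/0.5/0.7, complete data, no dyad effect, covariates left out, and effects in raw-score SDs. Let d1 and d3 be the between-arm differences in change at one and three months. Each estimate has variance (2/n) × 2(1−ρ), and their covariance is (2/n)(1−ρ). Hence:
- 2-df test: noncentrality = n(d1² − d1·d3 + d3²) / [3(1−ρ)], critical value 5.991.
- 1-df three-month contrast: z = d3 / √[4(1−ρ)/n], critical value 1.96.

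**3. No effect at either visit.** Noncentrality is 0 and both tests reject 5% of the time.

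**4. Effect at one month only.** For d1 = 0.39 and d3 = 0, the noncentrality is 108 × 0.1521 / [3(1−ρ)] = 7.82/10.95/18.25.

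| Setting (ρ = 0.3/0.5/0.7) | 2-df rule positive | Three-month contrast positive |
|---|---|---|
| 0.39 SD, 108 per arm | 71/85/98% | 5% |
| 0.195 SD, 108 per arm | 22/30/47% | 5% |
| 0.39 SD, 86 per arm (assumed 20% loss) | 60/76/94% | 5% |
| 0.195 SD, 86 per arm | 18/24/38% | 5% |

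If 0.39 is read in change-score SDs, equal correlation makes the two changes correlate 0.5. The noncentrality is then 54 × 0.1521 / 0.75 = 10.95, giving 85% at every ρ (30% for 0.195).

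**5. What resting the claim on the three-month contrast does to power** (108 per arm, larger effect 0.39 SD).

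| Pattern | 1 df | 2 df | Difference in points |
|---|---|---|---|
| Equal at both visits, or three months only; equal correlation | 68/82/96% | 71/85/98% | 2 to 3 lost |
| One-month effect half the three-month effect; equal correlation | 68/82/96% | 57/73/92% | 4 to 10 gained |
| Equal at both visits; correlations r, r, r² (r = 0.3/0.5/0.7), unstructured covariance | 56/65/81% | 63/76/93% | 7 to 12 lost |
| Full at one month, half at three months; equal correlation | 23/30/46% | 57/73/92% | 35 to 47 lost |

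The last row before rounding is 57.4 − 22.8 = 34.6, 73.0 − 29.9 = 43.0 (72.96 − 29.94) and 92.2 − 45.6 = 46.6. Subtracting the rounded percentages gives 34 to 46.

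**6. A side check on the interval.** SAP 4.5 names "Random effects for the clustering within participant across timepoints and by dyad" and states no other covariance structure. If these are random intercepts and the correlations decay as r, r, r² (both assumed), the model's standard error for the three-month contrast relative to the true one is √{[2(1−r) + (1−r²)] / [3(1−r²)]} = 0.920/0.882/0.852. The interval would be about 8/12/15% too narrow.

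**The case against.** The strongest case for the plan is that the joint test is a recognised opening step before visit-specific contrasts. It matches the null as worded and the protocol's plural follow-up periods, and it has correct size when nothing happens at either visit. All of that stands. The rule's conclusion names no visit, so it is true as worded even when the effect is at one month only. The three-month contrast is also contained in the interaction term and could be read from the fitted model. That stands too, but a contrast that can be estimated has not thereby been named as primary or promised with an interval.

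A second objection is that the rule belongs to H3. The missing sex interactions argue against this, and if it were so, H1 would have no decision rule at all.

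A third is cost. When a full early effect halves by three months, the arms do still differ at three months, and the single contrast loses a great deal of power. This stands, and it is a reason to keep the joint test as a reported result. It does not make that test an answer to the three-month question.

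A fourth is that demoting the only written rule after data are in hand invites a charge of selective choice. That also stands, and it shapes the fix.

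**Conclusion.** The point holds as a mismatch between the stated primary question and the only decision rule, together with an unpromised primary estimate. It should be fixed before the result is reported. Confidence is moderate. The mismatch is plain in the text, but the attachment of the rule to H1 is inferred, and every percentage beyond the 80% rests on assumed correlations, complete or assumed follow-up, and no dyad effect.

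Three stronger readings are tempting, and the documents do not support them:
- A reader might infer that the test is invalid or inflates the error rate. It does not. The 71/85/98% (22/30/47% at 0.195 SD) counts as error only if a significant interaction is presented as the three-month claim.
- A reader might infer that the joint test is simply the weaker one. It gains or loses power depending on how the effect develops over time.
- A reader might infer that the three-month interval will be too narrow. That needs both intercept-only random effects and decaying correlation, and the SAP states neither. It is a matter for a sensitivity check.

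**What to change.** In SAP 4.5:
- State that the primary claim rests on the model-based between-arm difference in change from baseline to three months (1 df, two-sided 0.05), reported with its 95% confidence interval.
- Keep the 2-df interaction and report it, with the one-month between-arm difference and its 95% interval.
- Say that a significant interaction alone does not support a three-month claim.
- Relabel the printed equation as the H1 model, and replace the word adherence with HIV stigma.

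In SAP section 2, align the primary null with the three-month outcome of section 1.

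Date the change and justify it by the SAP's own outcome definition. The SAP already reports sample results (enrolment in 3.1, no positive screens in 3.2.2, scale reliability in 4.2), so this is a change made after data were seen. Reporting the joint test whatever it shows limits any suspicion of selective choice.

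Optionally, as a sensitivity analysis, refit with an unstructured within-participant covariance that keeps the dyad effect, or use robust standard errors clustered by dyad. Clustering by participant alone would drop a level of clustering that the SAP names.

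The cost is text and one reported contrast, with no new data. The price in power is as tabulated: small in most patterns, and large if a full early effect half fades.
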